9.5 Treatment discontinuation

Patients may continue to receive study drug for as long as the investigator feels is appropriate, unless any of the following criteria are met:

- 1) Clinically and/or radiologically documented disease progression (as determined by RECIST 1.1 criteria);
- 2) The occurrence of unacceptable toxicity (including grade 4 pancreatitis, any myocardial infarction, embolic/occlusive cerebro-vascular accident (stroke) or need for revascularization procedure);
- 3) Failure to recover from hematological and/or non-hematological toxicity to re-treatment level despite dose modification and dosing interruption of up to 28 days;
- 4) Patient's request or Investigator's recommendation;
- 5) Patient death (complete Serious Adverse Event Report for deaths occurring within 30 days after last study drug dose OR for deaths occurring after 30 days, only if considered related to study drug).

However, in individual cases, after discussion with the PI/sponsor patients may continue to receive therapy past initial RECIST defined progression if the investigator feels that the patient is deriving ongoing benefit from the drug. In the event that this occurs, formal documentation of the progression event including the site of disease, the action taken and the reason why ongoing clinical benefit is proposed is required each time this occurs in any patient.

Following systemic progression, blood and optional repeat tumor sampling will be requested for retrospective analysis of potential mechanisms of acquired resistance. If CSF or other body fluids are sampled while on study, then the consent will cover exploratory analyses of these including, but not limited to those related to tumor and host biology and drug/drug metabolite levels.

10.0 ANALYSIS PLAN AND DATA CAPTURE

10.1 Estimated patient numbers

We aim to screen 700 patients in total in Part A (see Section 5 for details of calculation)

Study requirements, in terms of Part B enrollments: Accruing 13 patients for each 12 that will be evaluable.

22 (20 evaluable) patient FGFR1 double negative cohort (up to additional 36 across all cohorts, but likely mostly within FGFR1 double negative cohort if altered dosing required)

13 patient FGFR1 SISH+ve and ISH+ve cohort

13 patient FGFR1 SISH+ve and ISH-ve cohort

13 patient FGFR1 SISH-ve and ISH+ve cohort

13 patient RET+ve cohort

Estimate 74 patient (inc non-evaluable) on treatment study, up to 100 if additional biomarker cohorts are added to be explored.

Excess marker positive patients identified beyond the initial cohort accrual targets, will be directed towards additional expansion of cohorts (following additional support) if evidence of $ORR \geq 40\%$, other studies or remaining standard therapies as appropriate, while generating a larger natural history database relating to *FGFR1/RET* biology.

10.2 Part A Analysis Plan

The goal of Part A is to determine the prevalence of each biomarker and the overlapping frequency of biomarkers (primary objective), which will guide on-going screening for selecting biomarker positive patients for the clinical trial to be conducted in part B. The association between biomarker positivity and the patient clinical and pathological features will be studied (secondary objective) to guide the selection process. In addition, the effectiveness of prescreening locally and nationally will be estimated (secondary objective). Interim analyses will be conducted after 250 and 500 screened samples, before the final analysis, to inform ongoing screening strategies. We will compare and contrast these with the data available from planned and ongoing analyses of tissue microarrays. With 700 samples, the maximum width (distance from the lower limit to the higher limit) of 95% confidence interval for the prevalence of a biomarker will be 0.075.

Biomarker prevalence and its 95% (exact) confidence interval (CI) among the screening patients and for different histologies will be reported. Overlapping frequency and its 95% CI between biomarkers among the screening patients and for different histologies will also be reported. The association between biomarker positivity and clinical/pathological features will be assessed using chi-square test, or Fisher's exact test if necessary, with the features including histology, age at diagnosis of current lung cancer (using age groupings as a categorical variable where necessary), age at diagnosis of metastatic lung cancer, race, sex, current stage, sites of metastatic disease at diagnosis, smoking status, EGFR, KRAS and ALK status. Biomarker prevalence will be reported for each category of features significantly

associated with biomarker prevalence. We will determine the impact of biomarker results on prognosis generating Kaplan-Maier survival curves for overall survival using log-rank testing to compare the survival distributions between marker positive and negative patients for each biomarker. In addition, we will determine the impact of the biomarker results on sensitivity or resistance to standard chemotherapies and patterns of metastatic spread as we have done before (Camidge et al, 2011; Doebele et al, 2012).

The effectiveness of prescreening will be summary measures. Success of the nationwide approach will be defined by 50% of screening enrollments coming from outside Colorado, with 85% of marker positive patients enrolling into available cohorts of the intervention trial. No formal hypothesis testing will be performed. Summary statistics such as percentage and its 95% CI will be used to track and analyze the remote patients and local patients capture and enrollment as well as the barriers to remote patient accrual. Analyses contrasting remote outreach methodology with the numbers and proportions seen through traditional direct clinical contact will be descriptive in nature.

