of activity at 45mg, even if well tolerated, potentially lower doses (eg 30mg) may also be explored in the FGFR1 cohorts to mitigate safety in future studies. The National Cancer Institute Common Terminology Criteria for Adverse Events (NCI-CTCAE, Version 4.0) will be used to grade adverse events. A dose level will be considered tolerable following completion of 1 cycle (28 days) in 9 of 12 patients in the absence of dose limiting toxicity (DLT). If ≥ 3 patients experience DLT at this dose level, the dose level will be deemed non-tolerated. A DLT will be defined by the adverse events listed in Section 9 that are considered possibly, probably, or definitely related to ponatinib. If 45mg is not tolerated per DLT criteria, 30mg will be explored in the FGFR1 cohorts, assuming insufficient patients were treated at 45mg to assess efficacy accurately. As the IC50 for RET is an order of magnitude lower than for FGFR1, and the starting dose for the RET cohort will be 30mg, the logic relating to efficacious exposures for doses based on FGFR1 PD markers/responses will not automatically be applied to the *RET+* cohort and if activity in *RET+* cases is noted at the time this will not influence the decision-making re dose alteration in the *FGFR1+* cohorts. However, if ≤ 2 responses are seen in the initial *RET+* cohort but *FGFR1+* responses or FGFR PD modulation have been noted at 45mg and 45mg appears acutely well tolerated per DLT criteria we will reconsider this logic and accrue an additional *RET+* cohort at 45mg. If doses other than 45mg QD are explored, the number of patients in each biomarker selected cohort will be modified to include only those treated at the final ‘biologically selected dose’ (i.e. the tolerable dose associated with evidence of FGFR pathway pharmacodynamic modulation or of radiographic responses in FGFR biomarker selected cohorts) and the response rates in each biomarker selected cohort will be calculated within each cohort using only the number treated at this dose.

Objectives:

Primary:

Part A – To determine the prevalence of defined biomarkers in the screened patient populations.

Part B –To determine the objective response rate (ORR) (RECIST v1.1) to ponatinib in different molecularly defined cohorts of lung cancer.

Secondary:

Part A –

- 1) To determine the effectiveness of prescreening locally and nationally.
- 2) To determine the clinical and pathological features associated with biomarker positivity and negativity.

Part B –

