The goal of Part A is to determine the prevalence of each biomarker and the overlapping frequency of biomarkers (primary objective), which will guide on-going screening for selecting biomarker positive patients for the clinical trial to be conducted in part B. The association between biomarker positivity and the patient clinical and pathological features will be studied (secondary objective) to guide the selection process. In addition, the effectiveness of prescreening locally and nationally will be estimated (secondary objective). Interim analyses will be conducted after 250 and 500 screened samples, before the final analysis, to inform ongoing screening strategies. We will compare and contrast these with the data available from planned and ongoing analyses of tissue microarrays. With 700 samples, the maximum width (distance from the lower limit to the higher limit) of 95% confidence interval for the prevalence of a biomarker will be 0.075.

Biomarker prevalence and its 95% (exact) confidence interval (CI) among the screening patients and for different histologies will be reported. Overlapping frequency and its 95% CI between biomarkers among the screening patients and for different

histologies will also be reported. The association between biomarker positivity and clinical/pathological features will be assessed using chi-square test, or Fisher's exact test if necessary, with the features including histology, age at diagnosis of current lung cancer (using age groupings as a categorical variable where necessary), age at diagnosis of metastatic lung cancer, race, sex, current stage, sites of metastatic disease at diagnosis, smoking status, EGFR, KRAS and ALK status. Biomarker prevalence will be reported for each category of features significantly associated with biomarker prevalence. We will determine the impact of biomarker results on prognosis generating Kaplan-Maier survival curves for overall survival using log-rank testing to compare the survival distributions between marker positive and negative patients for each biomarker. In addition, we will determine the impact of the biomarker results on sensitivity or resistance to standard chemotherapies and patterns of metastatic spread as we have done before (Camidge et al, 2011; Doebele et al, 2012).

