- Based on literature data: FGFR1 SISH will be positive in 6% SCLC (no information available on ISH probability).
- RET will be positive in 2% adenocarcinomas. However, in a pan-negative adenocarcinoma/NOS population this is estimated at 20% based on internal data at CU and these patients will be prioritized internally for RET FISH testing after FGFR1 testing over those who have other markers positive.
- Based on literature data: ALK will be positive in 4% adenocarcinoma (excluded from testing in trial).
- Based on literature data (Western population): EGFR mutations will be positive in 10% adenocarcinoma (excluded from testing in trial)

We assume, for practical purposes, EGFR, ALK, RET and FGFR1 marker positivity will behave as if mutually exclusive.

We assume 85% of marker positive patients will enter treatment cohorts.

We assume 5% of patients will be non-evaluable on treatment.

To populate each cohort with 12 evaluable patients, therefore 15 positive patients need to be identified and 13 treated.

22 (20 evaluable) patient FGFR1 double negative cohort (up to additional 36 across all cohorts, but likely mostly within FGFR1 double negative cohort if altered dosing required)

13 patient FGFR1 SISH+ve and ISH+ve cohort

13 patient FGFR1 SISH+ve and ISH-ve cohort

13 patient FGFR1 SISH-ve and ISH+ve cohort

13 patient RET+ve cohort

This makes a total of 74 patients (inc non-evaluable) on the initial treatment study, with up to 100 if additional cohorts are added.

To populate these cohorts will require 700 patients to be screened for FGFR1 SISH and ISH and 266 by RET FISH.

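### Part A cannot estimate RET-FGFR1 overlap, because only FGFR1 double negatives go to RET FISH, and Section 10.2 gives RET no denominator or precision of its own

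*Combined protocol and SAP*

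**What the plan says.** The Synopsis gives the Part A primary objective as "To determine the prevalence of defined biomarkers in the screened patient populations". Section 10.2 widens it to the prevalence of each marker together with the overlap between markers.

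On precision, the sentence in the Synopsis and Section 10.2 opens "With 700 samples, the maximum width" and ends "95% confidence interval for the prevalence of a biomarker will be 0.075".

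On reporting, Section 10.2 makes one commitment for single markers: "Biomarker prevalence and its 95% (exact) confidence interval (CI) among the screening patients and for different histologies will be reported". Nothing there sets a denominator marker by marker.

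A second commitment concerns pairs of markers, and it leaves no pair out: "Overlapping frequency and its 95% CI between biomarkers among the screening patients and for different histologies will also be reported".

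Section 10.2 also looks outside the screen for a comparison: "We will compare and contrast these with the data available from planned and ongoing analyses of tissue microarrays".

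The numbers tested are in Section 5.5: "To populate these cohorts will require 700 patients to be screened for FGFR1 SISH and ISH and 266 by RET FISH". Sections 4.0, 5.2.2 and 5.5 restrict RET FISH to FGFR1 double negatives of adenocarcinoma or NOS histology (large cell is included in 5.2.2), and only where it is covered as standard of care. Internal cases must also be pan-negative on the site's other assays. For sizing, Section 5.5 assumes that "RET and FGFR1 marker positivity will behave as if mutually exclusive", and it leaves the check of that assumption to a tissue microarray (TMA) analysis.

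**The concern.** There are two gaps between the analysis plan and the screening algorithm.

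First, Section 10.2 promises an overlap estimate with a confidence interval for markers in general. For RET with either FGFR1 marker, the patients who could show overlap are the ones the algorithm does not send for RET FISH. The result would be zero whatever the true overlap, and an interval around it would restate the sizing assumption while looking like evidence for it.

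Second, the one precision statement is worded for any biomarker but rests on 700 results, and RET is not planned to have 700. Section 10.2 does not say whether RET prevalence is taken over those tested or over everyone screened. It also does not say how the internal and external streams, which the plan expects to have different RET rates, are to be presented.

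What is at stake is the meaning of figures reported under the Part A primary objective, not a treatment decision.

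**Working it through.** **Method.** Section 10.2 specifies exact intervals for prevalence. For x positives in n, the Clopper-Pearson limits are

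lower = Beta quantile(0.025; x, n − x + 1), upper = Beta quantile(0.975; x + 1, n − x).

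Width is upper minus lower. The maximum width is the largest value over x = 0 to n, reached at x = n/2.

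**Step 1: reproduce the plan's figure.** At n = 700 the maximum is 0.0754, at x = 350. This rounds to the stated 0.075, so the arithmetic is right.

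**Step 2: planned RET numbers (Table 10, years 1 to 4).**
- Internal tests: 10 + 20 + 20 + 20 = 70. Expected positives: 2 + 4 + 4 + 4 = 14.
- External tests: 28 + 56 + 56 + 56 = 196. Expected positives: 1 + 1 + 2 + 2 = 6.
- Total: 70 + 196 = 266 tests, matching Section 5.5, with 14 + 6 = 20 positives.

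**Step 3: RET precision at those numbers.**

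| RET result set | n | Maximum width | Expected x | Rate | Exact 95% CI | Width |
|---|---|---|---|---|---|---|
| Pooled | 266 | 0.123 | 20 | 7.5% | 4.7% to 11.4% | 0.067 |
| Internal pan-negative | 70 | 0.244 | 14 | 20% | 11.4% to 31.3% | 0.199 |
| External | 196 | 0.144 | 6 | 3.1% | 1.1% to 6.5% | 0.054 |

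At n = 266 the width is 0.0739 for x = 25 and 0.0751 for x = 26. The pooled width therefore passes 0.075 only from 26/266 = 9.8%.

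**Step 4: the denominator changes the answer.** The same 20 positives are 20/266 = 7.5% of those tested and 20/700 = 2.9% of all screened (width 0.026). The second figure counts untested patients as RET negative.

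**Step 5: the stream mix changes a pooled rate.** With internal share w and the two planned rates held fixed, pooled rate = 0.20w + 0.0306(1 − w).
- Planned share, w = 70/266 = 0.263: 7.5%.
- Assumed w = 0.20 (not in the documents): 0.0400 + 0.0245 = 6.4%.
- Assumed w = 0.40 (not in the documents): 0.0800 + 0.0184 = 9.8%.

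**Step 6: what can be cross-tabulated.**

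| FGFR1 result | RET FISH under the algorithm |
|---|---|
| SISH+ and/or ISH+ | not scheduled |
| SISH− and ISH−, adenocarcinoma or large cell/NOS | scheduled if covered as standard of care (internal cases: pan-negative only) |
| SISH− and ISH−, other histology | not scheduled |

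The cell that would hold RET-positive, FGFR1-positive patients is empty because no one in that row is scheduled for the test. No choice of interval method changes this. SISH and ISH, by contrast, are both planned in all 700, so their overlap can be estimated.

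Two routes could produce a RET result in an FGFR1-positive patient: outside assay results accepted case by case (Appendix A), and later RET FISH in atypical responders (Section 2.6). Both are incidental and selected, so they do not provide an overlap estimate.

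**The case against.** The strongest reply on precision is that the sentence is conditional on 700 samples and is true as written. Section 5.5 openly gives 266 for RET. The 0.123 maximum needs RET positivity near 50%, whereas the plan assumes 2% in adenocarcinoma and 20% in pan-negatives. All of this stands. A reader might infer that 0.075 is a miscalculation or that RET will miss it. The documents support neither inference: the figure reproduces, and the expected pooled width is 0.067. What remains is that RET has no stated precision or denominator in Section 10.2.

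On the denominator, Section 5.5 uses the word screened marker by marker, so prevalence among those tested is the natural reading. On pooling, no section commits to a single RET rate, and Table 10 keeps the streams apart. Both replies are fair. They show that the intended analysis is probably sensible, but Section 10.2 does not state it.

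On overlap, the plan labels exclusivity as an assumption, plans to test it on TMA data and adapt if needed, and commits in Section 10.2 to a comparison with TMA results. The overlap that defines the FGFR1 cohorts, SISH by ISH, is unaffected. This limits the harm, but it does not stop Section 10.2 from presenting a RET-FGFR1 zero as an estimate.

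Two stronger readings should be resisted:
- A reader might take all FGFR1-positive patients expected in Table 10 (35 + 56 + 98 = 189 of 700) as the number the FGFR1 restriction keeps from RET testing. Section 5.5 describes the SISH+ISH+ group as all squamous or squamous-behaving NOS, and about half of the SISH−ISH+ group likewise. The true squamous and SCLC cases would not receive RET FISH whatever their FGFR1 result.
- A reader might calculate an interval for 0/266 and say that the plan will report it. The plan names no such figure.

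**Conclusion.** The point holds and is minor. RET-FGFR1 overlap is zero by design under the prospective algorithm and is not estimable from Part A, yet Section 10.2 promises overlap with a 95% CI and excludes no pair.

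The 0.075 is correct for SISH at n = 700, and for ISH if all 700 are evaluable. RET needs its own statement: maximum 0.123 at n = 266 and 0.067 at the expected 20/266. A pooled RET rate also depends on how many results come from each stream.

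These figures assume that Table 10's counts are met. Fewer RET results are possible, because testing depends on standard-of-care coverage, Appendix A places RET last when tissue is short, and some results may be inconclusive. The maximum width would then exceed 0.123. The overlap conclusion does not depend on the counts.

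Part A is descriptive, and no Part B test or dose rule uses these quantities.

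**What to change.** In Section 10.2, the Synopsis and the table shells:

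1. Limit overlap estimation to SISH by ISH. State that RET-FGFR1 overlap is not estimable from Part A, refer that question to the TMA analysis already planned, and list any incidental RET results in FGFR1-positive patients descriptively.
2. Tie the 0.075 to FGFR1 SISH and ISH at n = 700. Add RET at n = 266: maximum width about 0.12, and about 0.07 at the expected count.
3. Define each marker's denominator as patients with an evaluable result for that marker, with inconclusive results shown separately. Report RET for the internal pan-negative and external streams separately. Label any pooled RET rate as conditional on who was tested and on the stream mix.

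The cost is editing only, with no extra patients or assays. The one drawback is a less favourable stated precision for RET.

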Patients will be grouped into one of 4 'bins' based on the expression of FGFR1 SISH and ISH biomarkers using the positive/negative cutpoints developed from cell line sensitivity data. FGFR1 SISH and ISH negative patients (FGFR1 double negatives) will then be further subdivided on the basis of histology. Adenocarcinomas and large cell/Not otherwise specified histologies who are FGFR1 double negative will receive RET FISH testing when covered as SOC. In addition, as the coordinating center for the LCMC, the vast majority of our internal CU adenocarcinoma patients and most other histologies have also already been profiled by *ALK/ROS1/MET* FISH and by SNaPshot analyses. For CU internal cases, *RET* FISH testing will be further restricted to only *FGFR1* double negative adenocarcinoma/NOS patients who are known to be pan-negative by these other assays. The RET FISH negative cases from this screen plus the remaining FGFR1 SISH and ISH negative histologies will be eligible for accrual into the FGFR1 double negative cohort. Five cohorts are planned (FGFR1 SISH+ISH+, FGFR1 SISH+ISH-ve, FGFR1 SISH-veISH+, FGFR1 SISH-veISH-ve (FGFR1 double negative cohort) and RET FISH+).

As mentioned above, in addition to the potential benefit from the treatment intervention in patients positive for one of the study's ponatinib-related markers, we will aim to increase the overall penetration of molecular testing and the understanding of the pros and cons of repeat biopsies to obtain sufficient material for testing in the wider medical and patient community by having a series of preprinted letters to send to patients involved in Part A as follows:

Letter #1 (Appendix G): Letter for patient to deliver to their treating MD in the event that they have insufficient available tumor material for molecular testing, discussing the need to ensure no other material from other samples remains that might be used, the likelihood of different markers being positive by clinical factors and the pros and cons of rebiopsy in these situations.

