Based on our experiences with several different biomarker selected trials in lung cancer, we anticipate approximately 50% of the screening enrollments to come from outside Colorado. This is feasible during the time scale of the study given our prior experience with *ALK*, but excessive use of screening resource on groups with low/no marker positive prevalence is undesirable if we wish to make maximum use of the available support. We have adopted some enrichment policies upfront, assuming *RET* changes will be mutually exclusive with *FGFR1* biomarkers, and similarly that all of these will be mutually exclusive with *EGFR* mutations and *ALK* rearrangements in adenocarcinomas. These assumptions will be tested in a TMA analysis and if the TMA data suggest that a significant proportion of marker positive patients are being missed by any of these approaches, we will adapt our strategy accordingly. As the coordinating center for the LCMC, the vast majority of our adenocarcinoma patients and most other histologies have already been profiled by *ALK/ROS1/MET* FISH and by SNaPshot analyses. The initial high *RET* positivity rate in our BJALCF funded project, looking in cases that are ‘pan-negative’ on these platforms, continues to suggest that mutual exclusivity predominates for most of the known oncogenic drivers in lung cancer. However, the existing clinical/TMA dataset for *FGFR1* biomarkers is less mature than for *RET* and we have already noted overlap with *KRAS* mutations in some cell lines. Consequently, beyond the exclusion of known *ALK+* or *EGFR* mutant adenocarcinomas, we have not mandated further enrichment strategies for *FGFR1* screening. Yet, for internal cases, to maximize yield we will continue to prioritize cases ‘pan-negative’ on our standard platforms for testing with *RET* FISH within this study. This means internally, we may not complete *RET* FISH testing on some *FGFR1* double negatives because of the presence of other known molecular drivers. Beyond capturing the molecular test results already conducted on each case, we will not be able to determine whether external cases have been similarly prioritized for any aspect of the screening or not. Because our internal cases are likely to have been more extensively profiled than those in the community, we have estimated a higher *RET* positivity rate for the patients we screen internally compared to those sent through the remote prescreen consenting process. Because we do not know the degree to which ‘pan-negatives’ will be prioritized for the *FGFR1* testing internally, or the overlap of *FGFR1* related biomarkers with most of the known oncogenic drivers in lung cancer, we have not assumed any specific alteration in marker positivity for internal as opposed to external cases. However, as data emerge, we will consider formally instituting practical enrichment for *FGFR1* biomarkers, ruling out some subgroups to screen if ≥ 100 patients of a

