APPENDIX A: BIOMARKER PRESCREENING

A1. Sample capture flowsheet

*Internal cases to d/w PI re RET FISH as pan-negatives to be prioritized

FGFR1 SISH, ISH and RET FISH are described. See Lab Manual for detailed Standard Operating Procedures. Comparable information derived from other assays, e.g. NGS platforms for RET rearrangements, may be permissible as an entry criterion, following discussion with the PI. In such cases, attempts to confirm with the study specific assays should be made.

Material sufficient for some but not all assays will still be considered acceptable and assays will be prioritized in the following order: *FGFR1* SISH, *FGFR1* ISH, *RET* FISH.

For equivocal or inconclusive cases, confirmatory assays (e.g. RT-PCR for RET rearrangements) may be conducted and if a conclusive result is generated, may be permissible as an entry criterion, following discussion with the PI.

Excess unstained slides of the requested 20 x 4uM and/or tumor block will be archived and consenting will permit additional biomarker analyses to be conducted pertaining to the biology of lung cancer and/or outcomes from this study.

A2. FGFR1 Copy number and message levels ([name] lab):

I. Protocol for SISH Assay

FGFR1 gene copy number is to be detected using Silver in Situ Hybridization (SISH) on the Benchmark® XT automated stainer (Ventana Medical Systems, Inc.). One unstained slide of the adequate ID is to be stained for FGFR1 SISH, and another unstained slide is to be reserved as backup in case of assay failure.

FGFR1/ CH8 SISH Procedure

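### RET prevalence in Part A should be reported separately for internal pan-negative and external cases, because one figure overall and by histology mixes two selection rules

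*Combined protocol and SAP*

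**What the plan says.** The synopsis and Section 1 give the Part A primary objective as "To determine the prevalence of defined biomarkers in the screened patient populations". Section 10.2 implements it: "Biomarker prevalence and its 95% (exact) confidence interval (CI) among the screening patients and for different histologies will be reported". It adds that the results will guide ongoing screening, with interim looks after 250 and 500 samples, and that with 700 samples the 95% CI for a prevalence will be at most 0.075 wide.

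RET FISH is not applied under one rule. Section 5.2.2 says that for internal University of Colorado (CU) cases "FISH testing will be further restricted to only" FGFR1 double-negative adenocarcinoma/NOS "patients who are known to be pan-negative by these other assays", meaning SNaPshot and ALK/ROS1/MET FISH. External cases must be FGFR1 double negative with adenocarcinoma or NOS histology, and EGFR- or ALK-positive adenocarcinomas are excluded. Section 5.5 says the team cannot tell whether external cases were prioritised in a similar way.

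Section 5.5 expects the streams to differ. It puts RET at 2% of adenocarcinomas, then says: "However, in a pan-negative adenocarcinoma/NOS population this is estimated at 20% based on internal data at CU". It also states that a higher rate has been assumed "for the patients we screen internally compared to those sent through the remote prescreen consenting process".

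The features listed in Section 10.2 for the association analysis run from histology and age to "sites of metastatic disease at diagnosis, smoking status, EGFR, KRAS and ALK status". Neither source (internal or external) nor pan-negative status is among them.

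**The concern.** A prevalence has meaning only for a stated population. Removing tumours with another known driver raises the RET rate among those that remain, and the sizing section relies on exactly that. An analysis that then gives one RET figure, overall and by histology, averages an enriched stream with one that is not required to be enriched. Histology cannot separate them, because both consist of adenocarcinoma and NOS cases.

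The stake is practical. The figure is meant to steer screening while the trial runs and to be compared with tissue microarray data. Section 5.5 requires 15 positives to fill a cohort. The number of RET tests this implies depends heavily on which rate is used, so a combined rate would mislead a decision about which stream to expand. No Part B hypothesis test or eligibility rule depends on it.

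**Working it through.** **Inputs (Table 10, years 1 to 4)**
- Internal RET tests: 10 + 20 + 20 + 20 = 70. Positives: 2 + 4 + 4 + 4 = 14.
- External RET tests: 28 + 56 + 56 + 56 = 196. Positives: 1 + 1 + 2 + 2 = 6.
- FGFR1 screening: 350 internal + 350 external.

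**Reproducing the plan's own figures**
- RET tests: 70 + 196 = 266, as stated in Section 5.5.
- Patients screened: 350 + 350 = 700, as stated.
- Maximum CI width at n = 700: the exact interval at 350/700 has width 0.0754 and the Wald interval 2 × 1.96 × √(0.25/700) = 0.0741, consistent with 0.075.
- Internal rate: 14/70 = 20%, as stated. The external rate is not stated. Table 10 gives 6/196 = 3.1%. The Section 5.5 and Figure 14 assumptions agree: 2% / (1 − 0.04 ALK − 0.10 EGFR − 0.22 FGFR1) = 2% / 0.64 = 3.1%.

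**Prevalence by stream, tested cases as denominator**

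The exact limits for x positives in n are the 2.5% quantile of Beta(x, n − x + 1) and the 97.5% quantile of Beta(x + 1, n − x).

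| Stream | Positive/tested | Rate | Exact 95% CI |
|---|---|---|---|
| Internal, pan-negative | 14/70 | 20.0% | 11.4% to 31.3% |
| External | 6/196 | 3.1% | 1.1% to 6.5% |
| Combined | 20/266 | 7.5% | 4.7% to 11.4% |

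The two stream intervals do not overlap, and the combined estimate lies outside both.

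**Dependence on the mix**

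With internal share s, the combined rate is s × 0.200 + (1 − s) × 0.0306.
- s = 10%: 4.8%
- s = 26% (70/266, as planned): 7.5%
- s = 50%: 11.5%
- s = 75%: 15.8%

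Table 10 holds the share at 26% every year (10/38, then 20/76). The combined figure therefore shifts for this reason only if actual testing departs from plan.

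**Consequence for screening**

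Tests needed for 15 positives: 15/0.200 = 75 internally, 15/0.0306 = about 490 externally, and 15/0.0752 = about 200 at the combined rate.

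**Denominator**

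If the denominator is everyone screened, the same positives give 20/700 = 2.9% (1.8% to 4.4%). The 0.075 width belongs to n = 700. At n = 266 the maximum exact width is 0.123 (at 133/266).

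**The case against.** **The plan never says it will pool, and it is not blind to source.** This is true. Pooling is inferred because Section 10.2 names no RET estimate other than overall and by histology. The feature list is introduced as inclusive rather than closed, home State and other molecular results are captured, and Sections 5.3 and 10.2 contrast remote with local patients. That contrast, however, concerns capture, enrolment and barriers under a secondary objective, and Section 5.3 records only whether any trial marker is positive. Remote or local consent is also not the same as pan-negative status.

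**The contrast depends on the denominator.** This stands. Over all screened, the streams are 14/350 = 4.0% (2.2% to 6.6%) and 6/350 = 1.7% (0.6% to 3.7%). These intervals overlap, and the ratio falls from 6.5 to 2.3. That reading counts untested cases as RET negative. Section 10.2 does not say which denominator it intends.

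**The planning rates are soft.** This also stands. The 20% matches 4 positives among 20 in-house patients (Section 3.3), with an exact 95% CI of 5.7% to 43.7%. With the external rate and mix held at plan, that range puts the combined figure between 3.8% and 13.7%. The external count comes from rounded yearly entries.

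**Stronger readings that the documents do not support.**
- A reader might infer that the combined figure reflects nothing but the mix. It depends on the stream rates as well.
- A reader might take external cases to be unselected. Section 5.5 says only that their prioritisation cannot be determined, and RET FISH is done only when covered as standard of care.
- A reader might infer from Appendix A that known RET positives would count as screened positives. The text says "Comparable information derived from other assays, e.g. NGS platforms for RET rearrangements, may be permissible as an entry criterion", after discussion with the principal investigator and with attempts at confirmation. That governs entry and is silent on the prevalence count.

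**Conclusion.** The point holds as a reporting gap in a primary analysis. Section 10.2 specifies RET prevalence in a form that merges a stream restricted to pan-negative cases with one that is not so restricted, although the sizing section treats them as having different rates. On the plan's counts the streams are 20.0% and 3.1%, and the combined 7.5% represents neither.

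The size rests on three assumptions: that Table 10's planned counts are realised, that the tested cases are the denominator, and that the overall and by-histology estimates are the only RET prevalences to be reported. The denominator is a separate ambiguity, moving the combined figure between 7.5% and 2.9%, and the stated precision does not apply to 266 tests.

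The documents do not support the conclusion that no combined figure may be given, or that patients with prior RET results must all be removed. Separate feature-association tests by stream would rest on about 14 and 6 positives and would tell little. The data needed for the split are already collected, so the defect can be mended before reporting, but the analysis should be specified in advance because it is meant to guide screening at the interim looks.

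**What to change.** In Section 10.2 and the synopsis:
1. Report RET prevalence with the number tested as denominator and an exact 95% CI, separately for (a) internal cases preselected as pan-negative and (b) external FGFR1 double-negative cases. Say of (b) that prior prioritisation is unknown.
2. If a combined figure is given, label it as the yield of the tested mix and state the internal share beside it.
3. State that the 0.075 maximum width applies to markers tested in all 700, and give the corresponding width for the RET denominator (0.123 at 266).
4. Flag patients whose RET-positive status was known before Part A consent, and add a sensitivity estimate that omits them.

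This is a wording change. Sections 5.2 and 5.5 already provide for collecting prior molecular results and distinguish internal from external cases. The cost is precision: the planned intervals are about 20 percentage points wide internally (31.3 − 11.4) and 5 externally (6.5 − 1.1), against 7 for the combined figure (11.4 − 4.7). The external interval is narrower in absolute terms only because its rate is low; relative to its estimate it is wider than the combined one.
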